10.2.1 SERIOUS ADVERSE EVENTS

Serious Adverse Event (SAE): An SAE, as defined by the NIH, consists of adverse events that result in death, require either inpatient hospitalization or the prolongation of hospitalization, are life-threatening, result in a persistent or significant disability/incapacity or result in congenital anomaly/birth defect. Other

important medical events, based upon appropriate medical judgment, may also be considered Serious Adverse Events if a trial participant's health is at risk and intervention is required to prevent an outcome mentioned.

All SAEs will be recorded on the Serious Adverse Events Form (Appendix B), documented in the UE/SAE log and reported to the IRB. The SAE Form will be completed by the study coordinator, and includes information relating to the onset and nature of the SAE, relationship to the study treatment, seriousness of the SAE, treatment required as a response to the SAE, and outcome. This form will be filed in the participant's folder at the resolution of the event. The study coordinator will complete the UE/SAE log (Appendix D) which includes information such as the date of the event, time at which the study team was informed of the event, details, when the IRB was notified, and the date that the SAE form was completed.

10.2.2 UNANTICIPATED PROBLEMS

Unexpected Events (UE) will be recorded on the UE/SAE log (Appendix D) and will include information such as the date of the event, when the study team was informed of this event, details of the event, when the IRB was notified, and whether the SAE form was completed. The IRB will be notified of each UE that may occur during the study.

The Office for Human Research Protections (OHRP) considers unanticipated problems involving risks to participants or others to include, in general, any incident, experience, or outcome that meets all of the following criteria:

- unexpected (in terms of nature, severity, or frequency) given (a) the research procedures that are described in the protocol-related documents, such as the IRB-approved research protocol and informed consent document; and (b) the characteristics of the participant population being studied;
- related or possibly related to participation in the research (in the guidance document, possibly related means there is a reasonable possibility that the incident, experience, or outcome may have been caused by the procedures involved in the research); and
- suggests that the research places participants or others at a greater risk of harm (including physical, psychological, economic, or social harm) than was previously known or recognized.

If an UE occurs the IRB will be notified and the study will be adjusted as needed to protect the health and safety of the participants. Depending on the nature of the UE, the research protocol, inclusion/exclusion criteria, and informed consent will be changed to reflect the possibility of this event reoccurring. During this time, no new participants will be recruited and the research procedures for currently enrolled participants will be stopped. Each UE will be recorded and reported throughout the study.

10.3 REPORTING PROCEDURES

We will be adopting the following table for reporting procedures:

What Event is Reported	When is Event Reported	By Whom the Event is Reported	To Whom the Event is Reported
Fatal or life-threatening unexpected, suspected serious adverse reactions	Within 24 hours of initial receipt of information	Investigator	Local/internal IRBs

Non-fatal, non-life threatening unexpected, suspected serious adverse reactions	Within 48 hours of initial receipt of information	Study Coordinator	Local/internal IRBs/Institutional Officials, DSMB
Unanticipated adverse device effects	Within 10 working days of investigator first learning of effect	Investigator	Local/internal IRBs
Unanticipated problem that is not an SAE	Within 7 days of the investigator becoming aware of the problem	Investigator	Local/internal IRBs/Institutional officials
All Unanticipated Problems	Within 30 days of the IRB's receipt of the report of the UP from the investigator	IRB	OHRP
		Investigator	External IRBs

11.3.1 REPORTING OF PREGNANCY

Pregnancy tests will be administered on the first session of the experiment to all women of child-bearing potential (CBP). After testing negative, the experiment can continue. On subsequent sessions, female participants will be asked if it is possible that they may have become pregnant since the previous session. If the participant responds yes, or is unsure, then a pregnancy test will be administered. Within the study target population (ages 18-35), menstruating females, regardless of age are considered "CBP". Women who have had a hysterectomy or a bilateral oophorectomy are not considered of "CBP". There are no studies that suggest TMS would interfere with pregnancy. However, should a participant become pregnant during the study, her participation will be immediately terminated.

10.4 TYPES AND DURATION OF FOLLOW-UP OF PARTICIPANTS AFTER ADVERSE EVENTS

Medical monitors and PI will follow up with participants within one week of an AE.

11 STATISTICAL PLAN

The statistician for this study is [name].

11.1 STATISTICAL ANALYSIS STRATEGIES

To control for non-specific effects of rhythmic TMS, we will use an active control: arrhythmic TMS (randomized inter-pulse-interval) that is matched to the target stimulation in number of pulses and temporal duration. All analyses will be run on the difference from condition-matched arrhythmic TMS. The key analysis is a two-way repeated-measures ANOVA with factors TMS frequency (theta vs alpha) and location (inferior-IPS vs anterior-MFG). Post-hoc t-tests will be run on a significant main effect of TMS frequency, TMS site, or interaction. We will use Tukey's adjusted significance for post-hoc testing to correct for multiple comparisons.

Primary outcome: working memory capacity. Two-way repeated-measures ANOVA run on the difference from arrhythmic TMS with factors (TMS site and TMS frequency). The direction of the retro-cue is held consistent for each site: for TMS to frontal cortex (anterior-MFG) the retro-cue to the right is used, and for TMS to parietal cortex (inferior-IPS) the retro-cue to the left is used. We hypothesize that theta frequency rhythmic TMS will improve behavioral performance when applied to anterior-MFG; i.e. a main effect of TMS frequency and/or an interaction between TMS frequency and cue. We hypothesize that alpha frequency rhythmic TMS will improve behavioral performance for retro-cue trials when applied to inferior-IPS; i.e. an interaction between TMS frequency and cue.

Primary outcome: Spectral power. We collected EEG recording during the delivery of rhythmic TMS. We hypothesize, based on previous studies with identical rhythmic TMS trains, that rhythmic TMS will entrain neural oscillations in the targeted frequency. We will quantify entrainment from rhythmic TMS by analyzing the spectral decomposition of the EEG signal during TMS and immediately after TMS. We will run a six-cycle Morlet wavelet convolution with the EEG signal to estimate spectral density (microvolts per hertz). We hypothesize that the amplitude of theta activity will be increased following theta rhythmic TMS relative to theta activity following arrhythmic TMS. Similarly, alpha amplitude will be increased following alpha rhythmic TMS relative to alpha amplitude following arrhythmic TMS. The direction of the retro-cue is held consistent for each site: for TMS to frontal cortex (anterior-MFG) the retro-cue to the right is used, and for TMS to parietal cortex (inferior-IPS) the retro-cue to the left is used. We hypothesize an interaction between TMS frequency and cue.

Primary outcome: response time. Two-way repeated-measures ANOVA run on the difference from arrhythmic TMS with factors (TMS site and TMS frequency). The direction of the retro-cue is held consistent for each site: for TMS to frontal cortex (anterior-MFG) the retro-cue to the right is used, and for TMS to parietal cortex (inferior-IPS) the retro-cue to the left is used. We hypothesize that theta frequency rhythmic TMS will improve behavioral performance (decreased response time) when applied to anterior-MFG; i.e. a main effect of TMS frequency and/or an interaction between TMS frequency and cue. We hypothesize that alpha frequency rhythmic TMS will improve behavioral performance (decreased response time) for retro-cue trials when applied to inferior-IPS; i.e. an

interaction between TMS frequency and cue.

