2.2 DOSE RATIONALE

TMS is a safe, non-invasive, widely-used tool that applies focal electric fields to the brain using magnetic coils placed on the scalp (Rossi et al. 2009). On the first session of the study, participants will receive a motor thresholding procedure in which electrodes are attached to the first dorsal interosseous muscle of the right hand. The contralateral motor cortex will be targeted by single pulses of TMS until a motor evoked potential (MEP) is generated: defined as a near-instantaneous increase muscle activity greater than 200 microvolts. Next, the intensity of single pulse TMS will be lowered until an MEP is generated on five out of ten pulses. This is defined as the participant's motor threshold (Rossi et al. 2009). For the subsequent stimulation days, participants will receive TMS at 120% of their motor threshold. Participants will receive trains of 5 pulses at 5 hertz, 10 hertz, or arrhythmic randomized pulse intervals not to exceed an inter-pulse-interval of 20 milliseconds. Between every train will be at least 5 seconds. An inter-train-interval of 5 seconds or greater allows for any residual effects of stimulation to return to baseline. This intensity, inter-pulse-interval, and inter-train-interval is well within the safety guidelines set forth for repetitive TMS (Wassermann, 1998; Rossi et al., 2009) and has been used in similar paradigms as the one described here (Thut et al. 2011; Hanslmayr et al. 2014; Albouy et al. 2017). EEG will be collected using the Geodesic 400 system (EGI INC., Eugene, OR, USA). Collecting simultaneous EEG and TMS does not pose any additional risk over TMS on its own. EEG does not involve brain stimulation and is used purely for neuroimaging (minimal risk).

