4.1 TREATMENT ASSIGNMENT PROCEDURES

The three frequencies of interest (theta, alpha, and arrhythmic) are randomly intermixed within every task block. The randomization is uniquely generated for each participant and session. The order of regions targeted (a-MFG and i-IPS) will be randomized and counterbalanced across participants. The primary analysis of the experiment is to analyze the frequency specific effect of rhythmic TMS versus arrhythmic TMS within the same session. Therefore, the experiment is designed such that sequence order is irrelevant as every analysis is performed as a within session difference. Using neuro-navigation software, precludes a double-blinding as the experimenter must be aware of the targeted region. The participant will not be keen to the anatomical differences between these regions that are separated by only a few centimeters.

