6.2 SPECIAL ASSAYS OR PROCEDURES

Each participant will receive stimulation on all four sessions, separated by a week. The baseline session will involve single pulse TMS for calculating the motor threshold. The other three sessions will involve train of rhythmic TMS during performance of a cognitive control task. For stimulation day, the rhythmic TMS trains are delivered on every trial of the task (there are 600 trials per session). Each train of TMS consists of 5 pulses. There will be a total of 2400 pulses delivered per session. Each TMS train will be separated by a minimum of 5 seconds. There are three possible trains: alpha frequency with a 100 milliseconds inter-pulse interval, theta frequency with a 200 milliseconds inter-pulse interval, and arrhythmic with a variable inter-pulse interval (not to exceed a minimum of 20 milliseconds inter-pulse interval). The inter-pulse interval, inter-train interval, number of trains, and TMS intensity are all under the safety guidelines set forth by Rossi et al. 2009 and is typical for experiments that deliver online TMS (Hanslmayr et al. 2014; Albouy et al. 2017).

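### The duration-matching claim for the arrhythmic control does not fit the train descriptions; with one control length, rhythmic-versus-arrhythmic contrasts mix rhythm with train length

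*Combined protocol and SAP*

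**What the plan says.** - Section 11.1 calls arrhythmic TMS an active control that is "matched to the target stimulation in number of pulses and temporal duration". It runs every analysis on the difference from arrhythmic TMS matched to condition. Its key analysis is a two-way repeated-measures ANOVA of frequency (theta, alpha) by site (frontal, parietal).
- Section 6.2 describes the trains: "Each train of TMS consists of 5 pulses", and "There are three possible trains: alpha frequency with a 100 milliseconds inter-pulse interval, theta frequency with a 200 milliseconds inter-pulse interval, and arrhythmic". The arrhythmic interval is variable, with 20 ms given as a minimum. No total length is given.
- Section 2.2 words the same limit as "arrhythmic randomized pulse intervals not to exceed an inter-pulse-interval of 20 milliseconds", which reads as a maximum.
- Section 4.1 randomizes three frequency conditions, one of them arrhythmic, and says the primary analysis is to "analyze the frequency specific effect of rhythmic TMS versus arrhythmic TMS within the same session".
- Section 2.3.1 defines the compatibility effect from theta-minus-alpha differences (frontal) and alpha-minus-theta differences (parietal). It contains no arrhythmic term.

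**The concern.** The arrhythmic train is there to isolate rhythm: same pulses, same duration, no regular timing. That works only if its duration equals that of the train it is compared with. The two rhythmic trains differ in length by a factor of two, and the plan lists one arrhythmic type without stating its length, how many versions exist, or which arrhythmic trials serve as control for which rhythm.

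The contrasts at stake are not minor. The spectral-power hypotheses in Section 11.1 compare theta power after theta TMS, and alpha power after alpha TMS, with the same band after arrhythmic TMS. They are measured during the train and just after it, so the result can depend on when the pulses fall and stop. Six wavelet cycles nominally cover 6/5 = 1.2 s at 5 Hz and 6/10 = 0.6 s at 10 Hz, so train length affects which pulses lie inside the estimate. Section 11.2 sizes these contrasts separately, at 44 participants for theta and 21 for alpha.

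**Working it through.** **Inputs.** Section 6.2: 5 pulses per train; intervals of 100 ms (alpha) and 200 ms (theta); one arrhythmic type. Section 2.2: the 20 ms limit in its other wording. The plan states no train length, so there is no figure of its own to reproduce on this point. The sample size of 48 in Section 11.2 does reproduce (paired t-test, effect size 0.532, two-sided 0.05 assumed, power 0.9505), but nothing below depends on it.

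**Step 1: train length, first to last pulse = (pulses − 1) × interval.**
- Alpha: 4 × 100 = 400 ms.
- Theta: 4 × 200 = 800 ms.
- Arrhythmic, Section 2.2 read literally: at most 4 × 20 = 80 ms.
- Arrhythmic, Section 6.2: at least 4 × 20 = 80 ms, with no upper limit given.

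Section 6.2 also gives 2400 pulses over 600 trials, which is 4 per train, although 600 × 5 = 3000. With 4 pulses the lengths are 300 and 600 ms; the 2:1 ratio stays.

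**Step 2: mismatch for one common control length L.** Alpha: 400 − L. Theta: 800 − L. Their difference is (800 − L) − (400 − L) = 400 ms for any L.

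| L (ms) | Alpha mismatch (ms) | Theta mismatch (ms) |
|---|---|---|
| 400 | 0 | +400 |
| 600 | −200 | +200 |
| 800 | −400 | 0 |

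The larger of the two absolute mismatches is smallest at L = 600, where both are 200 ms. So at least one is always 200 ms or more.

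**Step 3: where control length enters.** Write T, A and R for the theta, alpha and arrhythmic means at one site, with that site's fixed cue.
- T − R and A − R each contain R, so each carries its own mismatch.
- (T − R) − (A − R) = T − A. A shared R drops out of the single-site theta-alpha comparison, the frequency main effect and the interaction. On simulated data with n = 48, the interaction and the main effect were the same with and without subtraction (largest difference 9e-16).
- The compatibility effect of Section 2.3.1 contains no R.

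**Step 4: where the rhythmic trains' own lengths enter.** Let bF and bP be the effect of an 800 ms rather than a 400 ms train at the frontal and parietal sites.
- Single-site theta minus alpha: shifted by bF or bP.
- Frequency main effect: shifted by (bF + bP)/2.
- Compatibility effect: shifted by (bF − bP)/2, which is zero if the effect is the same at both sites with their fixed cues.

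**Step 5: cost of two matched versions (trial noise only, m trials per train type now).**
- Arrhythmic trials halved: √[(1/m + 2/m)/(2/m)] = √1.5 = 1.22.
- Four train types with equal shares, each 3m/4: √[(8/3m)/(2/m)] = √(4/3) = 1.15.
- Theta minus alpha formed through two halved controls: √[(1 + 1 + 2 + 2)/2] = √3 = 1.73 times the standard error of the direct difference.

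**The case against.** The best defence is that Section 6.2 lists categories of train, not individual trains. The arrhythmic interval is variable, and Section 11.1 speaks of matching to the target and to the condition, so an alpha-length and a theta-length version may both be intended. This stands as a possibility: a reader might infer that the control is shown to be unmatched, and the documents do not show that. They do not settle the matter the other way either, since matching to condition could mean only same site and same cue, and no section mentions two versions or a pairing rule.

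Four other stronger readings also fail:
- A 400 ms mismatch for at least one frequency. This needs a control equal to one rhythmic train; a 600 ms control leaves 200 ms each way.
- A 720 ms mismatch (800 − 80). It rests wholly on the literal Section 2.2 wording, which Section 6.2 contradicts.
- Pulses falling closer to the probe in one condition. No section gives train onset, delay length or alignment to cue or probe.
- A biased main test. Control length cannot reach the interaction or the compatibility effect (Step 3), and the interaction is what the sample size of 48 rests on.

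**Conclusion.** Sections 2.2, 4.1, 6.2 and 11.1 do not fit together on the arrhythmic control. The finding is an inconsistency with a conditional consequence. If there is one common length, the alpha and theta mismatches differ by 400 ms, at least one is 200 ms or more (300 and 150 ms if trains have 4 pulses), and each rhythmic-minus-arrhythmic contrast mixes rhythm with train length. That covers the spectral-power hypotheses in 11.1 and the primary analysis as worded in 4.1. How far train length changes memory, response time or power cannot be derived from the documents.

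The interaction, the frequency main effect and the compatibility effect are free of any bias from a shared control. The 800 versus 400 ms difference between the rhythmic trains themselves remains in the frequency main effect and in single-site theta-alpha comparisons. It reaches the interaction only if its effect differs by site or cue.

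**What to change.** Reconcile Sections 2.2, 4.1, 6.2 and 11.1, including the direction of the 20 ms limit and the pulse count. State the arrhythmic length or lengths and which arrhythmic trials are subtracted from which rhythm. Then take one of two routes.

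1. **If the matching claim in 11.1 stands:** generate an alpha-length and a theta-length arrhythmic version within the reconciled limit, and compare each rhythm with its own version. Keep the direct theta-minus-alpha difference, as Section 2.3.1 defines it, for the interaction, and amend the sentence in 11.1 that puts every analysis on the arrhythmic difference. This avoids the 1.73 factor, but leaves any site- or cue-specific length effect in the interaction, which should be acknowledged.
2. **If a single length stands:** delete the duration-matching claim and report rhythmic-versus-arrhythmic contrasts as confounded with train length.

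Route 2 costs only wording. Route 1 needs a change to the stimulus script and no extra trials, but leaves fewer arrhythmic trials per version. The trial-noise standard error of each rhythmic-versus-arrhythmic contrast rises about 22% if arrhythmic trials are halved, or about 15% with four equal shares. Assuming equal splits over three train types and three cues, halving takes arrhythmic trials per cue from about 67 to 33 at the 600 trials of Section 6.2. At the 200 to 300 trials implied by Section 6.5.1 (10 blocks of 20 to 30), it takes them from about 22–33 to 11–17. Those two trial counts need reconciling before choosing.

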2.3 STUDY AIMS/HYPOTHESES

2.3.1 PRIMARY OUTCOME – WORKING MEMORY CAPACITY

RATIONALE. Participants make a button press on a keyboard to indicate if the probed items are matched or non-matched to the items held in memory. The investigators will calculate the accuracy for these responses and convert this to Pashler's working memory capacity metric for each condition. Theta oscillations are known to be generated in frontal cortex when cued to the contralateral visual field. Alpha oscillations are known to be generated in parietal cortex when cued to the ipsilateral visual field.

ALTERNATIVE HYPOTHESIS. When the frequency of TMS to either frontal or parietal cortex is compatible with the endogenous activity, working memory capacity should increase relative to TMS that is incompatible. Therefore, we will report the TMS compatibility effect as the average of "theta minus alpha TMS to frontal cortex for retro-cue right" and "alpha minus theta TMS to parietal cortex for retro-cue left". We will report the mean and standard deviation of the TMS compatibility effect across participants. This effect will be investigated using repeated-measures two-way ANOVA, and an interaction between TMS site and TMS frequency is hypothesized.

NULL HYPOTHESIS. There is no systematic effect of frequency specific TMS on working memory capacity.

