2.3.2 PRIMARY OUTCOME – SPECTRAL POWER

RATIONALE. The electrical activity of the brain is recorded during performance of the task and during brain stimulation. The investigators will perform Morelet wavelet convolution on the recorded electrical signal to calculate the spectral power of theta (5-8 hertz) and alpha (8-12 hertz). Theta oscillations are known to be generated in frontal cortex when cued to the contralateral visual field. Alpha oscillations are known to be generated in parietal cortex when cued to the ipsilateral visual field.

ALTERNATIVE HYPOTHESIS. When the frequency of TMS to either frontal or parietal cortex is compatible with the endogenous activity, spectral power in the stimulated frequency band should increase relative to TMS that is incompatible. Therefore, we will report the TMS compatibility effect as the average of "theta power for theta minus alpha TMS to frontal cortex for retro-cue right" and "alpha power for alpha minus

theta TMS to parietal cortex for retro-cue left". We will report the mean and standard deviation of the TMS compatibility effect across participants. This effect will be investigated using repeated-measures two-way ANOVA, and an interaction between TMS site and TMS frequency is hypothesized.

NULL HYPOTHESIS. There is no systematic effect of frequency specific TMS on spectral power.

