4 BASIC STUDY DESIGN

This study is a pilot, four-session study with TMS and EEG to understand the neural oscillatory basis of cognitive control. Participants will perform a cognitive control task in which a retro-cue is used to distinguish between relevant and irrelevant lateralized stimuli that need to be accurately recalled for testing in each trial. The rhythmic TMS manipulation targets the previously localized EEG frequencies and previously localized regions of the brain from MEG (Wallis et al., 2015). The frequencies of stimulation will be theta (5 hertz), alpha (10 hertz), and arrhythmic. The regions of stimulation will be anterior-MFG, inferior-IPS. The study consists of an initial screening session, a baseline session, and two counterbalanced stimulation sessions with TMS delivered during task performance. During the initial screening session, participants will learn and perform the cognitive control task at varying levels of difficulty in order to titrate their performance accuracy. During the baseline session, participants will perform the titrated cognitive control task while EEG is recorded. The motor threshold (MT) for each participant will also be calculated either on this day or during the Stimulation 1 session. MT is calculated by placing the TMS coil at a 45-degree angle from the midline along the central sulcus (just above the ears). An electrode is attached to the contralateral first dorsal interosseous muscle. Then the primary motor cortex is stimulated with single pulse TMS until a motor evoked potential (MEP) is generated in the contralateral hand muscle, defined as a near-instantaneous increase in electrical activity above 200 microvolts. Then the intensity of TMS is lowered until an MEP is evoked on five out of ten pulses. Additionally, visible hand twitches may be used as instead of visual twitches to determine MT. The MT allows for TMS to be calibrated to the particular sensitivity level of the individual participant's brain. On the subsequent TMS session we will stimulate at 110% of MT. We ensure that TMS is driving neural activity but that this activity is within the range of endogenous activity and hence is at an appropriately safety level according to guidelines established for TMS (Rossi et al. 2009). On the third and fourth session (Stimulation 1 and Stimulation 2) the anterior-MFG and inferior-IPS is targeted by rhythmic TMS during performance of the cognitive control task. The sequence of TMS targets will be randomized and counterbalanced across participants. However, it is not possible to double-blind the study because the location of the TMS coil needs to be aligned to the targeted brain region with neuro-navigation software (Localite, Sankt Augustin, Germany). In other words, the region targeted by TMS is necessarily visible to the experimenter for accurate targeting. The study will be single blinded as the participant will not know the anatomical differences between the targeted regions and the position on the scalp differs by only a few centimeters between each site. Critically, the manipulation of interest is the frequency of stimulation. On each trial, the frequency will be randomly selected, counter-balanced, and inter-mixed. The effects of rhythmic TMS do not last for more than a few cycles beyond stimulation itself (Thut et al. 2011; Hanslmayr et al. 2014; Albouy et al. 2017). Therefore, the experimental design randomly intermixes the frequency of stimulation within every task block. The critical analysis is the within participant comparison of frequency specific TMS effects for a single site. The sequence order of target sites will have no impact because all analyses will be run as a difference from our active control (arrhythmic TMS) from within the same session. In addition, a brief resting-state EEG recording will be collected at the beginning of the

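### Rhythmic versus arrhythmic TMS is called the primary analysis, but section 11.1 names no test of that difference for any outcome

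*Combined protocol and SAP*

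**What the plan says.** Section 4.1 states: "The primary analysis of the experiment is to analyze the frequency specific effect of rhythmic TMS versus arrhythmic TMS within the same session". Section 4 describes the lead comparison this way: "The critical analysis is the within participant comparison of frequency specific TMS effects for a single site".

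Section 11.1 makes the difference from arrhythmic TMS the analysis variable ("All analyses will be run on the difference from condition-matched arrhythmic TMS"). It then names as key a two-way repeated-measures ANOVA with frequency (theta, alpha) and site (anterior-MFG, inferior-IPS). Arrhythmic is not a factor level, and the cue direction is fixed within each site. Follow-up is conditional and Tukey-adjusted: "Post-hoc t-tests will be run on a significant main effect of TMS frequency, TMS site, or interaction".

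Sections 2.3.1 to 2.3.3 define the compatibility effect without an arrhythmic term. For working memory the alternative is that "working memory capacity should increase relative to TMS that is incompatible".

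Section 11.1 also predicts that rhythmic TMS will improve behaviour, and that theta and alpha amplitude will exceed their levels after arrhythmic TMS. Section 11.2 sizes the two EEG comparisons with arrhythmic TMS (effect sizes 0.56 and 0.83).

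**The concern.** The comparison that section 4.1 calls primary, and that section 11.2 sizes for EEG, has no test statistic, no named cells and no error allocation in section 11.1. Subtracting arrhythmic TMS does not supply the test. Every effect in the ANOVA compares difference scores with each other, never with zero.

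What is at stake is the conclusion. A site-by-frequency interaction looks the same whether matched TMS raises performance above the active control, mismatched TMS lowers it below the control, or both happen. A significant interaction supports the statement that compatible TMS is better than incompatible TMS, which is the alternative in section 2.3. It does not by itself support the improvement, or the increase over arrhythmic TMS, predicted in section 11.1.

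**Working it through.** **1. The plan's own figures.** The inputs are the effect sizes and sample sizes in section 11.2. A repeated-measures interaction with one degree of freedom is a one-sample t-test on a per-participant contrast, so power comes from the noncentral t with n − 1 degrees of freedom and noncentrality d√n. The plan does not state the level; two-sided 5% is assumed.

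| Comparison | d | Stated n | Power at stated n | Power at n = 48 |
|---|---|---|---|---|
| Working memory interaction | 0.532 | 48 | 0.9505 | 0.9505 |
| Theta EEG vs arrhythmic | 0.56 | 44 | 0.953 | 0.967 |
| Alpha EEG vs arrhythmic | 0.83 | 21 | 0.951 | over 0.999 |

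All three stated sample sizes are reproduced.

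**2. What each contrast measures.** Write θ, α and r for theta, alpha and arrhythmic TMS, and F and P for frontal and parietal, with the cue fixed by site.

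- Compatibility: C = ½[(θF − αF) + (αP − θP)]
- Matched minus arrhythmic: M = ½[(θF − rF) + (αP − rP)]

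The ANOVA interaction tests C. Nothing in section 11.1 tests M or either of its components.

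**3. Illustration.** Assume equal independent cell errors with variance σ² and one arrhythmic cell per site. Then Var(C) = ¼ × 4σ² = σ², Var(M) = σ², Cov(C, M) = ¼ × 2σ² = ½σ², so their correlation is 0.5. Set d = 0.532 for C. If a share b of the effect is benefit of matched TMS and the rest is harm by mismatched TMS, the effect size for M is 0.532b: 0, 0.266 or 0.532. With n = 48 and two-sided 5% (joint results from 200,000 simulated trials):

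| Split | Interaction significant | M significant | Interaction significant, M not |
|---|---|---|---|
| All harm | 95% | 5% | 91% |
| Half benefit | 95% | 44% | 52% |
| All benefit | 95% | 95% | 4% |

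The split is an assumption; the documents give no information on it.

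**4. Does the subtraction change the interaction?** This depends on a point the documents leave open.

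- *One arrhythmic train type for both frequencies.* Section 4.1 lists three intermixed conditions, and section 6.2 says "There are three possible trains". Then (θ − r) − (α − r) = θ − α at each site. The arrhythmic term cancels exactly from the frequency effect and the interaction for working memory capacity and response time. On simulated data the interaction F was 1.830521 with and without subtraction. The same holds for EEG power if the band is fixed by site, as in "theta power for theta minus alpha TMS to frontal cortex for retro-cue right". The site effect keeps the arrhythmic data but only compares sites.
- *Two duration-matched arrhythmic versions.* Section 11.1 describes the control as "matched to the target stimulation in number of pulses and temporal duration". Five pulses span 4 × 100 = 400 ms at 10 Hz and 4 × 200 = 800 ms at 5 Hz, so one duration cannot match both. With two versions the term does not cancel. The variance of C on subtracted scores becomes ¼ × 8σ² = 2σ². If 0.532 was measured on unsubtracted scores, d falls to 0.532/√2 = 0.376 and power to 72%; if it was measured on subtracted scores, power stays at 95%. Section 11.2 does not say which.
- *EEG band following the TMS frequency.* The term does not cancel.

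In all three cases no difference from arrhythmic TMS is tested against zero.

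**The case against.** The formal alternatives in section 2.3 are compatible against incompatible TMS. The ANOVA tests exactly those, and section 4.1 can be read as explaining why session order does not matter. For EEG, sections 11.1 and 11.2 give the measure, direction, comparator and sample size, and the sample sizes reproduce as paired t-tests, so the gap is close to one of naming. Section 11.1 does not list its follow-up contrasts, so it is an inference from Tukey's method that they compare cells with each other. These points narrow the issue but do not close it. Section 4.1 uses the word primary, section 11.1 predicts improvement and increases over arrhythmic TMS, and for working memory and response time neither a test nor a sizing against arrhythmic TMS is given.

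Four stronger readings are tempting, and the documents do not support them:

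- *The arrhythmic control drops out of the key analysis.* This is only one of two open readings, and the duration matching in section 11.1 points the other way.
- *The plan names three rival lead comparisons.* Each stimulation session targets one site, so the single-site comparison in section 4 and the within-session comparison in section 4.1 can be the same. The conflict is between those two sections and section 11.1.
- *The ANOVA is invalid or the sample size is wrong.* Neither follows; both stand for the interaction.
- *The EEG comparisons are underpowered.* They are well powered at n = 48.

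**Conclusion.** The concern holds: the comparison that section 4.1 calls primary has no specified test for any outcome, and the one named test cannot stand in for it. This should be fixed before analysis, because it decides what may be claimed from a significant result. If the effect were all harm by mismatched TMS, about 91% of trials would show a significant interaction without a significant gain over arrhythmic TMS; with an even split, about 52%. Those percentages rest on equal independent cell errors, one arrhythmic cell per site, d = 0.532, n = 48 and two-sided 5%. The absence of the test, and the inability of the interaction to separate benefit from harm, do not depend on those assumptions. The cancellation of the arrhythmic term is a secondary point, conditional on how many arrhythmic train types exist and how the EEG band is chosen.

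**What to change.** 1. **Section 11.1.** For each outcome, prespecify a one-sample test against zero, with estimate and 95% CI, of the mean of theta minus arrhythmic (frontal, cue right) and alpha minus arrhythmic (parietal, cue left), with the two single-site components as follow-up. For EEG use theta power and alpha power respectively. For response time a benefit is negative. Run it whatever the ANOVA shows, and state how error is shared with the interaction, for example by Holm or in a fixed order chosen by the sponsor.
2. **Wording of conclusions.** Report a significant interaction alone as better than incompatible TMS. Reserve improvement, or increase relative to arrhythmic TMS, for a significant rhythmic-minus-arrhythmic test.
3. **Reconcile.** Sections 4 and 4.1 with section 11.1 on which comparison is primary; sections 4.1 and 6.2 with section 11.1 on whether there are one or two arrhythmic train types.
4. **Section 11.2.** State that the 95% power for working memory covers the interaction only, and that no working memory effect size against arrhythmic TMS is given. State that the EEG figures are for single comparisons, not the pooled contrast: at n = 48, 96.7% (d = 0.56) and over 99.9% (d = 0.83) at an unshared two-sided 5%, or 93.7% and over 99.9% at a 2.5% step.

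**Cost.** One contrast per outcome, on arrhythmic trials already intermixed in every block; no added participants or sessions. Under the illustration, running both tests at 5% gives about 9% false rejection per outcome under the global null. Holm keeps this under 5%. Interaction power becomes 91–94% instead of 95%, and power for the new contrast becomes 94% instead of 95% (all benefit) or 43% instead of 44% (half benefit). This shares error within an outcome only; error across outcomes needs its own statement.
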